Exclusion criteria:	
 1. Type 1 diabetes or diabetes clearly identified as having monogenetic etiology (e.g.: MODY). 2. Steroid-induced diabetes if steroid use is on-going or most recently taken within the last 3 months. 3. Pregnancy, plans to become pregnant within 6 months, or breast-feeding 4. Any use of insulin in the previous year. 5. Current or previous use of isCGM or rtCGM. 6. Cognitive dysfunction (SPMSQ score ≥ 5). 7. Symptoms of acute metabolic decompensation (extreme thirst, high urinary output, and weight loss, accompanied by acute fatigue or dyspnea). 8. Any terminal condition that would limit life expectancy to < 1 year. 9. Inability or refusal to use isCGM (e.g.: afraid of the device). 10. Inability or refusal to be reached by telephone. 11. Concurrent participation in another diabetes-related trial. 12. Has not already received two doses of a Health Canada-approved vaccine against SARS-CoV-2.
Evaluation criteria	
Primary Outcome: Change in glycated hemoglobin (HbA1c) at 3 months compared to baseline.
 
Secondary Outcomes: Feasibility of recruitment Blood pressure, body weight, waist circumference, and patient-reported outcomes, measured as change in continuous score at 3 months compared to baseline on validated instruments of:
 
 • Diabetes treatment satisfaction • Diabetes self-management empowerment • Diabetes-related distress • Diet • Physical activity

	Safety Outcomes: Any reported adverse events, major adverse events – hospitalization or ED visits. isCGM-related reactions (e.g.: skin reactions).
Treatment	Following informed consent, eligible adults will be randomly allocated to isCGM + education and feedback with a certified diabetes educator (CDE) or enhanced usual care with education and feedback using a 1:1 allocation ratio. The intervention (isCGM or enhanced usual care) will last 6-8 weeks. Those in the isCGM arm are free during the intervention or afterwards to obtain or fund their own supplemental isCGM sensors.
Randomization	Patients will be randomly assigned using a REDCAP based randomization system using variable block size. The computer-generated allocation table would be generated in a formal and secure manner.

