4. STUDY OBJECTIVES

Primary Objective

To evaluate the effectiveness of isCGM with CDE education and feedback on glycemic control at 12 weeks, in adults with type 2 diabetes and uncontrolled HbAc ($> 7.0\%$) not on insulin therapy.

Secondary Objectives

To determine the feasibility of recruiting adults with diabetes in Edmonton-area to a trial of glucose self-monitoring and education.

To determine the effectiveness of isCGM with CDE education and feedback on patient self-management of diabetes, measured using patient reported instruments for diabetes-related quality of life, diabetes treatment satisfaction, diabetes self-management empowerment, diet, and physical activity – at 6 weeks and at 12 weeks.

To determine the safety of isCGM with CDE education and feedback with respect to emergency department visits or hospitalizations, and isCGM-specific reactions (e.g.: skin reactions).

To understand the reasons *why* or *how* isCGM with CDE education is effective or ineffective from the perspective of involved participants and their providers.

To evaluate the effectiveness of isCGM with CDE education and feedback on glycemic control at 24-52 weeks (post-trial observational follow-up).

5. isCGM (INTERMITTENTLY SCANNED CONTINUOUS GLUCOSE MONITOR) – DESCRIPTION OF TECHNOLOGY

Technology – The only isCGM on the market at this time is the FreeStyle Libre 2 system produced by Abbott. FreeStyle Libre 2 sensors use a subcutaneous, wired enzyme glucose-

sensing technology, factory-calibrated to detect glucose levels in *interstitial* fluid by way of a thin filament implanted under the skin. The sensors are water-proof, affix to the skin by medical adhesive, last 14 days each, and are roughly the size of two stacked quarters. They measure interstitial glucose every minute, with readings stored in 15-minute intervals. Patients can scan sensors on-demand, using either a near-field communication-enabled smart phone or the FreeStyle Libre 2 Reader, to receive a glucose result along with historic results for the preceding 8 hours. The FreeStyle Libre 2 system is fully marketed in Canada; in 2020, it's predecessor, the similar FreeStyle Libre flash glucose monitoring system, had over 2 million users internationally.³²

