10. STUDY OUTCOMES AND VARIABLES

Case report forms are provided in Appendix 5. These will be translated into electronic documents to be completed by participants via a password protected webportal (EpiCore).

Primary Outcome:

- Change in HbA1c at 12 weeks compared to baseline.

Secondary Outcomes:

- Feasibility of recruitment
 - Participant referral, screening, and randomization rates over time
 - Reasons for inclusion / exclusion of all participants referred.
- Change in scores at 6 and 12 weeks compared to baseline, on the patient-reported outcomes shown in Table 1, below.
- isCGM participants only – change in time-in-target range, coefficient of variation, and glucose management indicator at 12 weeks compared to baseline.

Table 1: Patient-Reported Outcomes

Outcome	Instrument	Number of items
Diabetes treatment satisfaction – Status score	Diabetes Treatment Satisfaction Questionnaire (DTSQs) ³⁷ (weeks 6 and 12)	8
Diabetes treatment satisfaction – Change score	Diabetes Treatment Satisfaction Questionnaire (DTSQc) (week 6 only)	
Self-management empowerment	Diabetes Empowerment Scale – Short Form (DES-SF) ³⁸ (weeks 6 and 12)	8
Diabetes-related distress	Problem Areas in Diabetes (PAID) Questionnaire ³⁹	20
Diet	UK Diabetes and Diet Questionnaire (UKDDQ) ⁴⁰ (weeks 6 and 12)	25
Physical activity	International Physical Activity Questionnaire (IPAQ) short form ^{41,42} (weeks 6 and 12)	7
Health status	Euroqol EQ-5D-5L (weeks 6 and 12)	5

* In addition to collection at baseline.

Safety outcomes at 12 weeks:

- Any adverse events (serious and non-serious) occurring from baseline to 12 weeks will be identified and tracked at the 12 week study visit by patient interview, and reviewed

by study investigators to determine whether clinically attributable to diabetes, diabetes management, or isCGM. isCGM issues (e.g.: skin reactions) will be specifically sought.

- Emergency department visits or hospital admission for any reason, identified from patient interview and from NetCare review.

Qualitative Outcomes: Semi-structured interviews will undergo thematic analysis using constant comparative methods. The starting point will be the participant and provider experience with isCGM or enhanced usual care, with a particular focus on barriers and enablers of effectiveness (see Appendix 6, interview guides). Semi-structured interviews will take place for participants after trial completion (from 12-24 weeks).

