14. STATISTICAL AND ANALYTICAL METHODS

Our sample size calculation was intended to detect an HbA1c difference of 0.5%, presuming a standard deviation of HbA1c values at 3 months of 0.78% based on a recent similar trial of capillary blood glucose monitoring. To have 80% power to detect this HbA1c difference at a type 1 error rate of 5%, we would need 40 trial-completers in each arm. Given expected loss-to-follow-up rates of 20% or more, our enrollment target will be 100 participants.

Data will be analyzed according to intention-to-treat principles. Patients will be kept in the study group to which they were randomized, and efforts will be taken to ascertain outcome events in all patients randomized. Discontinuation of study treatment (isCGM) or no-show to CDE encounters are not equivalent to withdrawal from the study, and efforts will be made to contact study participants for HbA1c measurements and patient-reported outcomes at 12 weeks regardless.

Outcomes (HbA1c and patient-reported outcomes) are continuous scores – the difference at 12 weeks from baseline will be presented using simple means and standard deviations. On change in HbA1c, our primary outcome, we will test for a difference between intervention and enhanced usual care arms using linear regression with adjustment for age and sex. Secondary outcomes and diabetes-related distress will be analyzed in similar fashion, including follow-up values for patient-reported outcomes obtained at 6 and 12 weeks. Safety outcomes are dichotomous (e.g.: ED visits), and differences between trial arms will be assessed using Fisher's exact test. The primary outcome will be considered statistically significant at $p < 0.05$. Secondary and safety outcomes are considered hypothesis-generating and will also be considered statistically significant at $p < 0.05$. No correction for multiple comparisons is planned *a priori*. If the primary outcome is statistically significant at $p < 0.05$, the Benjamini-Hochberg procedure will be performed on secondary outcomes targeting a false discover rate of 20%, if requested by reviewers.

Secondary analyses are planned, and include:

- Post-hoc analysis of outcomes in clinically relevant groups, e.g.: by sex, baseline self-management empowerment, etc., using the above methods.

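### Six patient-reported scores are collected at weeks 6 and 12, but the only model named is a single-visit regression of change, which leaves week-6 information out of the week-12 comparison, and the time point differs between sections

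*Combined protocol and SAP*

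**What the plan says.** Section 14 tests the primary outcome, change in HbA1c, "using linear regression with adjustment for age and sex". For the other outcomes it adds one sentence: "Secondary outcomes and diabetes-related distress will be analyzed in similar fashion, including follow-up values for patient-reported outcomes obtained at 6 and 12 weeks". It names no visit term, no within-person covariance, no baseline-score covariate and no method for missing scores. It does state intention-to-treat, and it promises efforts to contact participants for 12-week questionnaires whether or not they kept to the intervention.

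The time point of the patient-reported outcomes is given differently in different places:

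- Synopsis, Evaluation criteria: "measured as change in continuous score at 3 months compared to baseline on validated instruments of" a list of constructs. No week-6 outcome is mentioned.
- Section 4, secondary objectives: "at 6 weeks and at 12 weeks".
- Section 10: "Change in scores at 6 and 12 weeks compared to baseline, on the patient-reported outcomes shown in Table 1, below".
- Section 14, descriptive summary: "the difference at 12 weeks from baseline will be presented using simple means and standard deviations". The testing sentence then covers both visits.

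Appendix 5.4 schedules DTSQs, DES-SF, PAID, UKDDQ, IPAQ and EQ-5D-5L at baseline, week 6 and week 12. The PAID row of Table 1 shows no week. DTSQc is collected at week 6 only and has no baseline value.

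**The concern.** A regression of one change score on arm handles one follow-up value per person, and these instruments have two. The natural reading of section 14 is one regression per visit. The week-12 regression then rests on people who returned a week-12 questionnaire and makes no use of the week-6 score of those who did not, although that score is the most recent information on them. The synopsis expects 20-30% loss to follow-up.

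Three things are at stake. Some precision is given up. The week-12 difference could be biased if those who leave after week 6 differ in their week-6 scores, and differ by arm; the trial is open-label, so this cannot be excluded. And because the sections disagree on the time point, the main patient-reported contrast is not fixed in advance, while section 12-week and 6-week results can each be declared significant at p < 0.05 and the analysts are not blinded. Self-management is part of the study hypothesis (section 3) and a named secondary objective (section 4).

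**Working it through.** **1. The plan's own figure.** The documents size only HbA1c: difference 0.5, SD 0.78, 80% power, 5% type 1 error (taken as two-sided).

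- Normal approximation: n per arm = 2 × (1.960 + 0.842)² × 0.78² / 0.5² = 2 × 7.849 × 0.6084 / 0.25 = 38.2, so 39.
- The t-test version gives 39.2, so 40, as stated. 80 completers / 0.80 = 100 enrolled.

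The sample size reproduces and this point does not touch it. No SD, correlation or sample size is given for any patient-reported score, so what follows rests on assumed ranges.

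**2. Precision, if loss is unrelated to the scores.** Let n1 be the number with week 6, n2 the number with week 12 (all of whom also have week 6), and ρ the correlation between the two follow-up values as modelled. In large samples, the variance of the week-12 estimate using both visits, relative to week-12 completers only, is

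ratio = 1 − ρ² × (n1 − n2) / n1.

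Assume 100 enrolled and that half of those lost have a week-6 score.

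| Loss | n1 | n2 | (n1 − n2)/n1 | Variance cut, ρ = 0.5 | Variance cut, ρ = 0.8 |
|---|---|---|---|---|---|
| 20% | 90 | 80 | 0.111 | 2.8% | 7.1% |
| 25% | 87.5 | 75 | 0.143 | 3.6% | 9.1% |
| 30% | 85 | 70 | 0.176 | 4.4% | 11.3% |

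Over wider assumptions (ρ 0.3 to 0.8; 25% to 100% of those lost having week 6; 20% or 30% loss), the gain in effective sample size runs from 0.5% to 24%.

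**3. Bias, if loss depends on the week-6 score.** Assumed: true difference 5 points at both visits, SD 15, ρ = 0.7, 25% lost in each arm. In the first two columns, low week-6 scores raise the chance of loss in the control arm only, with the logit slope per SD shown, and the other arm loses people at random. In the middle column, half of the loss occurs at random before week 6. In the last column, both arms have the same slope and all loss is after week 6. Simulated completer difference at week 12:

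| Logit slope per SD | Control arm only, all loss after week 6 | Control arm only, half of loss after week 6 | Same mechanism in both arms |
|---|---|---|---|
| 0.25 | 4.4 | 4.6 | 5.0 |
| 0.5 | 3.7 | 4.3 | 5.0 |
| 0.8 | 3.1 | 3.9 | 5.0 |
| 1.0 | 2.8 | 3.7 | 5.0 |

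An estimate that uses the week-6 scores returns 5.0 (to within simulation error) in every cell, because in this set-up loss depends only on observed values.

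**4. Baseline score.** The named model adjusts change for age and sex only. With equal variances σ² and baseline-to-follow-up correlation r, the variance of change is 2σ²(1 − r), against σ²(1 − r²) when the baseline score is a covariate. The ratio of the second to the first is (1 + r)/2, which is below 1 whenever r < 1. Adjusting for baseline is therefore at least as precise, and it removes chance baseline imbalance.

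**The case against.** The strongest reply is that section 14 is short rather than wrong. It nowhere says that people without a week-12 score are excluded. Change at 6 weeks is itself an outcome, so such people still count in a week-6 regression. Section 14 commits to pursuing 12-week questionnaires, and section 16 lets participants finish them from home. The 20-30% loss was used to plan HbA1c completers and is not an estimate of missing questionnaires. The outcomes are secondary and labelled hypothesis-generating. All of this stands, and it limits the point to the week-12 comparison under the model named.

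Three stronger readings are tempting and are not supported:

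- **That anyone missing week 12 is lost from the analysis altogether.** This would be read into silence. What follows from the named model is only that they leave the week-12 regression.
- **That both visits go into one ordinary regression as if independent.** Type 1 error would then be 2 × [1 − Φ(1.96/√(1 + ρ))], or 11% to 14% for ρ of 0.5 to 0.8. But section 10 defines change at each visit and nothing mentions pooling them, so this figure describes an analysis the plan does not set out.
- **That the week-12 result will be biased.** No passage says that controls will leave out of disappointment. Completer bias needs dropout related to the week-6 score differently by arm. When both arms behave alike, the table shows none.

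It is also fair to say that section 4 deliberately sets two time points, so making week 6 merely supportive would change an objective. That choice belongs to the investigators.

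**Conclusion.** The point holds as a matter of analysis choice and consistency. The only model named does not link the two follow-up visits, does not adjust for the baseline score and carries no rule for missing scores. The synopsis differs from sections 4 and 10 on the time point.

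The precision at stake is modest: about 4 to 9% of variance at 25% loss, if half of those lost have week 6 and the correlation is 0.5 to 0.8. The protection against bias is the better reason to change, but it is conditional: the completer estimate of an assumed 5-point difference ranges from about 2.8 to 5.0 depending wholly on the assumed dropout mechanism. SD, correlation, dropout slope and the share with week 6 are assumptions; the documents give none of them.

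The primary HbA1c analysis and the sample size are unaffected. The hypothesis-generating label lowers the stakes but does not settle the matter, since the same paragraph still applies a p < 0.05 threshold to these outcomes.

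**What to change.** In section 14, replace the sentence on secondary outcomes, as far as it concerns patient-reported scores, with wording to this effect:

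> Each patient-reported instrument with both follow-up visits (DTSQs, DES-SF, PAID, UKDDQ, IPAQ, EQ-5D-5L) will be analysed with one mixed model for repeated measures, with arm, visit, arm-by-visit, baseline score-by-visit, age and sex as fixed effects and an unstructured within-person covariance. The arm difference will be reported at week 6 and at week 12. DTSQc will be compared between arms at week 6 only, by linear regression adjusted for age and sex, without a baseline score.

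The investigators should then name the main time point for these outcomes and make the synopsis and sections 4, 10 and 14 agree with it. The week entries for PAID in Table 1 should be filled in to match Appendix 5.4.

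The cost is SAP wording and one model per instrument, with no new data. The downside is slightly more analysis work and reliance on loss being explained by the observed data (arm, age, sex, baseline and week-6 scores). A short sensitivity analysis for missing scores would show how far the week-12 result leans on that.

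### The 12-week safety comparison is planned as a Fisher's exact p-value alone; a risk difference with a 95% confidence interval should be added, because a non-significant result says little at 50 per arm

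*Combined protocol and SAP*

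**What the plan says.** One of the secondary objectives in section 4 is "To determine the safety of isCGM with CDE education and feedback with respect to emergency department visits or hospitalizations", together with sensor-specific reactions. Section 10 lists two kinds of safety outcome at 12 weeks: adverse events of any seriousness, collected by interview at the 12-week visit, and "Emergency department visits or hospital admission for any reason, identified from patient interview and from NetCare review".

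Section 14 gives the analysis in one sentence: "Safety outcomes are dichotomous (e.g.: ED visits), and differences between trial arms will be assessed using Fisher's exact test". It then adds: "Secondary and safety outcomes are considered hypothesis-generating and will also be considered statistically significant", at p<0.05. For these outcomes it names no effect measure, interval, expected event risk or power. By contrast, HbA1c and the patient-reported scores are to be analysed by linear regression, which produces an estimated difference between arms.

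Two other parts of the protocol bear on safety. Section 13 has investigators review and adjudicate every emergency visit and hospitalization up to week 12. Section 14 also plans regression of health care utilization on allocation, but only in the post-trial cohort.

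**The concern.** The objective asks how safe the intervention is on events that either arm can have. The only planned between-arm result is whether a p-value falls below 0.05. In a small trial with uncommon events, p>0.05 is the expected result whether or not the intervention raises the risk, so that result alone barely separates harm from no harm. What a reader needs is how large an excess the data still allow, and nothing in the plan produces that figure. Section 17 discusses the 20% type 2 error for HbA1c but not the much larger one for safety. Section 23 expects the results to bear on public insurance funding, so the safety statement will be read.

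Sensor skin reactions are not at issue here, since they do not depend on a between-arm test.

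**Working it through.** **Inputs from the documents**
- Enrolment: "our enrollment target will be 100 participants" (section 14). The synopsis gives "enhanced usual care with education and feedback using a 1:1 allocation ratio", so 50 per arm.
- Completers: "at a type 1 error rate of 5%, we would need 40 trial-completers in each arm" (section 14). Emergency visits and admissions are also looked up in NetCare, so close to 50 per arm may be evaluable; 40 is the less favourable case.
- Test and threshold: Fisher's exact test, p<0.05. Sidedness is not stated; two-sided is assumed.

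**Assumed, because the documents give no figure**
- Control 12-week risk: 2% to 20%, with 5% to 10% as the working case.
- Effect of interest: a doubling of risk.

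**Step 1. The plan's own sample size.** n per arm = 2 × (1.96 + 0.84)² × 0.78² / 0.5² ≈ 38.2, so 39. The plan states 40, at which the t-test has 81% power. 80 completers / 0.80 = 100 enrolled. The HbA1c calculation reproduces, and it is the only basis for the sample size.

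**Step 2. Power of the safety test.** Power is the sum, over all tables (x, y) with Fisher p<0.05, of Bin(x; n, p₀) × Bin(y; n, 2p₀). Type I error is the same sum with p₀ in both arms.

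| Control vs isCGM risk | Power, 50/arm | Missed, 50/arm | Missed, 40/arm | Type I error, 50/arm |
|---|---|---|---|---|
| 2% vs 4% | 0.6% | 99.4% | 99.8% | 0.04% |
| 5% vs 10% | 6.3% | 93.7% | 95.7% | 0.7% |
| 10% vs 20% | 19.5% | 80.5% | 83.8% | 1.8% |
| 15% vs 30% | 35.4% | 64.6% | 71.9% | 2.4% |
| 20% vs 40% | 51.5% | 48.5% | 59.2% | 2.8% |

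At 50 per arm, the smallest significant splits are 0 vs 6, 1 vs 8, 2 vs 10 and 5 vs 14.

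**Step 3. Test or sample size?** Share of trials at 50 per arm that fail to detect the doubling:

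| Risks | Fisher | Uncorrected chi-square | Newcombe 95% interval includes zero |
|---|---|---|---|
| 5% vs 10% | 94% | 86% | 89% |
| 10% vs 20% | 81% | 70% | 73% |

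Fisher's conservatism costs about 8 to 11 percentage points against chi-square. The rest is sample size. By the usual two-proportion formula, 80% power for a doubling needs 435 per arm at 5% vs 10% and 199 per arm at 10% vs 20% (474 and 219 with continuity correction).

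**Step 4. What an interval would add.** Newcombe's method combines the Wilson limits (l, u) of each arm: lower = d − √[(p₁ − l₁)² + (u₂ − p₂)²], upper = d + √[(u₁ − p₁)² + (p₂ − l₂)²].
- 10/50 vs 5/50: the Wilson limits are 0.112 to 0.330 and 0.044 to 0.214. With d = 0.10, lower = 0.10 − √(0.0077 + 0.0129) = −0.043 and upper = 0.10 + √(0.0170 + 0.0032) = 0.242. Fisher p = 0.26. The p-value says only that the result is not significant; the interval runs from −4.3 to +24.2 percentage points.
- 5/50 vs 5/50: d = 0, and the interval is ±√(0.0129 + 0.0032), or −12.7 to +12.7 points. Equal counts still leave an excess of over 12 points compatible with the data.

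**The case against.** The strongest reply is that a 100-patient trial sized for HbA1c cannot resolve uncommon events by any method, and that the plan does not claim it can. Step 3 bears this out: the proposed interval would itself include zero in 73% to 89% of trials under a doubling. Fisher's test is a standard choice for sparse counts. This reply stands against any suggestion that the test itself is the defect. It does not remove the case for an interval, whose purpose here is to show the remaining uncertainty and not to raise power.

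Second, the plan labels safety outcomes hypothesis-generating. A reader might infer that it will in effect declare no safety difference. The documents do not support that: no passage says p>0.05 will be read as safety or as no difference. Even so, the sentence with that label also applies the 0.05 threshold, and the label does not supply an estimate.

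Third, safety does not rest on the p-value alone. Sections 10 and 13 and the form in Appendix 5.6 provide for review of events, including relatedness, expectedness and seriousness, and section 13 requires the protocol to be reviewed if the trial caused a serious event. That is a real part of the safety answer for a licensed device with no serious adverse events expected. But it judges causality event by event, by investigators who are not blinded, and does not quantify the difference in all-cause visits or admissions. The post-trial regression does not fill the gap either, since section 17 concedes that it loses the balance of randomization.

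Finally, nothing forbids adding intervals at the reporting stage. That is true, and it is a reason to treat the point as minor.

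**Conclusion.** The point holds as a minor improvement to the analysis plan. Fisher's exact test at p<0.05 is the only 12-week between-arm analysis planned for safety outcomes, and no effect estimate or interval accompanies it.

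The miss rate for a doubling, about 80% to 94%, rests on three assumptions: a control risk of 5% to 10%, 50 evaluable per arm, and a two-sided test. It should not be read as a property of the plan itself, because the documents give no event risk; over 2% to 20% the range is about 48% to 99%. The conclusion does not turn on the exact figure, since even at 20% vs 40% about half of true doublings would be missed. The primary outcome, data collection and case-level safety review are unaffected.

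**What to change.** In section 14, replace the sentence on Fisher's exact test with text that still covers all the between-arm safety outcomes:

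> For any adverse event, any emergency visit, any hospital admission, and either of the latter two, the number and percentage of randomised participants with at least one event will be given by arm with the risk difference and 95% confidence interval (Newcombe or Miettinen-Nurminen). Fisher's exact p-values are descriptive, and p>0.05 will not be described as absence of a safety difference.

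In the later sentence that begins "Secondary and safety outcomes are considered hypothesis-generating and will also be considered statistically significant", delete the words *and safety*, so that section 14 does not apply a threshold it has just removed.

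The cost is two edits in section 14 and one extra column in the safety table. No new data, sample size change or change to patient care is needed. The downside is that the published safety statement will look visibly less certain.

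### The subgroup analyses specify no interaction test; if two equal subgroups both have the 0.5-point design effect, within-group tests disagree on significance about half the time

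*Combined protocol and SAP*

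**What the plan says.** Section 14 (Statistical and Analytical Methods) opens its list of further analyses with "Secondary analyses are planned, and include", and the first item is "Post-hoc analysis of outcomes in clinically relevant groups, e.g.: by sex, baseline self-management empowerment, etc., using the above methods".

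For the primary outcome, change in HbA1c, the method that this item points back to is: "we will test for a difference between intervention and enhanced usual care arms using linear regression with adjustment for age and sex". Significance is judged at p < 0.05. The other continuous outcomes are handled in similar fashion, and dichotomous safety outcomes by Fisher's exact test.

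The section names no treatment-by-subgroup interaction, and none appears elsewhere in the document. It gives no cut-point for the empowerment score and no closed list of groups. It plans no multiplicity correction; the optional Benjamini-Hochberg step covers secondary outcomes only.

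**The concern.** Whether isCGM works better in one group than in another is a question about the difference between two treatment effects. A two-arm test inside each group does not address it. Each test asks whether that group's effect differs from zero, and each has far fewer participants than the trial was sized for. One significant and one non-significant result can therefore arise easily when the two effects are identical.

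The instruction is also incomplete. In its own first example, sex, the age-and-sex-adjusted model cannot be fitted unchanged, because sex is constant within each group. For empowerment, the grouping could be settled after the data are seen. The analyses are introduced as planned and then called post-hoc, and the list is open-ended, so a reader of the results could not tell which subgroups were chosen in advance.

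At stake is a possible mistaken statement about who benefits from isCGM. The primary analysis is not affected.

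**Working it through.** **Inputs from the document**
- Effect: "Our sample size calculation was intended to detect an HbA1c difference of 0.5" (percentage points of HbA1c).
- SD: "presuming a standard deviation of HbA1c values at 3 months of 0.78" (percentage points). This is the SD of the 3-month values; the SD of the change is not given.
- Type 1 error 5% and power 80%; sidedness is not stated.
- Completers: "we would need 40 trial-completers in each arm", so 80 in total.
- Allocation: "using a 1:1 allocation ratio" (Synopsis, Treatment).
- Expected loss to follow-up: 20-30% of 100 enrolled (Synopsis, Sample size), which leaves 80 down to 70 completers.

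**Assumptions**
- Tests are two-sided.
- 0.78 serves as the SD of the analysed outcome.
- Subgroups split evenly, giving 20 completers per arm in each. The document gives no split, so a range is shown.
- A two-sample t-test stands in for the adjusted regression.

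**Step 1. The plan's own figure.** By the normal approximation, n per arm = 2 × (1.960 + 0.842)² × 0.78² / 0.5² = 38.2, so 39. By the exact t-test, power is 79.8% at 39 per arm and 80.8% at 40, so 40 per arm reproduces. Enrolment is 80 / (1 − 0.20) = 100.

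**Step 2. Power inside one subgroup.** With 20 per arm, effect 0.5 and SD 0.78, the noncentral t distribution gives p = 50.6% (52.7% by the normal approximation).

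**Step 3. Chance that exactly one subgroup is significant.** The subgroups contain different people, so the tests are independent:

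P = p₁(1 − p₂) + p₂(1 − p₁)

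For an even split this is 2 × 0.506 × 0.494 = 0.50. A simulation of 40,000 trials also gave 50.0%.

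**Step 4. Dependence on the true common effect** (80 completers, even split)

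| Common effect (points) | Power per subgroup | Exactly one significant |
|---|---|---|
| 0 | 5.0% | 9.5% |
| 0.1 | 6.8% | 13% |
| 0.25 | 16.7% | 28% |
| 0.5 | 50.6% | 50% |
| 0.75 | 84.2% | 27% |
| 1.0 | 97.7% | 5% |

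For equal groups, 2p(1 − p) cannot exceed 50%, so the design effect sits at the maximum.

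**Step 5. Dependence on the other assumptions** (common effect 0.5)
- Split of 80 completers: 51% at 60/40, 55% at 70/30, 62% at 80/20. For 80/20 the arithmetic is 0.714 × 0.777 + 0.223 × 0.286 = 0.62.
- Completers, even split: 49.6% with 70, 47.9% with 100.
- SD, even split and 80 completers: 38% to 50% over an assumed range of 0.6 to 1.2.

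**Step 6. The interaction test.** With equal true effects it rejects at its nominal 5% whatever the common effect is; the simulation at an effect of 0.5 gave 5.2%. Its standard error with four cells of 20 is 0.78 × √(4/20) = 0.349 points. Power for a true 0.5-point difference in effect is about 29% (30% by the normal approximation). The difference detectable with 80% power is (1.960 + 0.842) × 0.349 = 0.98 points.

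**The case against.** Four points can be made for the plan.

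*The text does not exclude an interaction term.* Linear regression can carry one, and a sex-adjusted model that cannot run within one sex suggests loose wording rather than a settled stratified procedure. This stands as far as it goes. Separate within-group tests are the natural reading, not an explicit statement, and a reader who concludes that the plan rejects interaction testing goes beyond the text. A plan should still not leave its subgroup method to inference.

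*The plan never says it will compare p-values.* Correct. A reader might infer that the trial will declare a differential effect whenever one group is significant and the other is not, but section 14 contains no such rule. The 50% is a rate of disagreement in significance. It becomes comparable with the 5% only if disagreement is read as a difference in effect.

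*The analyses are labelled post-hoc, and secondary outcomes hypothesis-generating.* This limits the consequence. However, the second label is attached to outcomes rather than to subgroups, the same list is introduced as planned, and a label does not make a within-group p-value answer a between-group question. Section 23 does say that the results may bear on public insurance funding, but it speaks of the trial as a whole and makes no claim about subgroups.

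*An interaction test would rarely find anything.* Also true: the detectable difference of 0.98 points is nearly twice the design effect. That is a reason to report effects with confidence intervals and to state the limitation. It does not support using a test that answers a different question.

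**Conclusion.** The concern holds in a conditional form. The plan specifies no test of whether the isCGM effect differs between subgroups, and its most natural reading is the two-arm regression repeated within groups, which for sex cannot be run as written.

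At the design effect of 0.5 points in both of two equal subgroups, those tests would give one significant and one non-significant result about 50% of the time, and 51-62% for splits of 60/40 to 80/20. This rests on an assumed split and on using 0.78 as the SD of the analysed outcome.

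It is tempting to say that any two subgroups with the same true effect will look different half the time. The calculation does not support that: the rate is about 10% with no effect, 28% at 0.25, 27% at 0.75 and 5% at 1.0. The within-group approach is weak because its disagreement rate moves with an unknown effect, whereas an interaction test keeps its false-positive rate at 5%.

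The change should be made, but the consequence is confined to secondary, partly self-labelled post-hoc analyses.

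**What to change.** In section 14, replace the closing reference to the methods above with wording such as:

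> by adding an arm-by-moderator interaction term, with the moderator's main effect, to the primary regression in all participants. For sex, the arm effect with 95% CI in each sex and the interaction p-value will be reported. For baseline empowerment, the score will be kept continuous; the interaction coefficient with 95% CI and the estimated arm effect at the 25th and 75th percentiles will be reported.

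The named percentiles matter because a continuous moderator has no per-subgroup effect until values are chosen; other values would serve if fixed now.

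Name sex and baseline empowerment as the planned moderators, and label every other subgroup analysis post-hoc and exploratory. This also removes the conflict between planned and post-hoc.

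The cost is a few sentences. Nothing changes in recruitment, data collection or sample size. The downside should be stated in the plan: at 80 completers the interaction test has about 29% power for a 0.5-point difference in effect, so a non-significant interaction is not evidence that the effect is the same in both groups.
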